[figure not shown]
Small Volume Bolus Of Papaverine versus Heparin To Maintain Patency Of Peripheral Arterial Catheters In Pediatric Patients Undergoing Surgical Procedures: Randomized, Controlled Trial, Double-Blind,Pilot Study

NCT03894904

Version Date: 08/05/2019

Title: Small Volume Bolus Of Papaverine versus Heparin To Maintain Patency Of Peripheral Arterial Catheters In Pediatric Patients Undergoing Surgical Procedures: Randomized, Controlled Trial, Double-Blind,Pilot Study.

Principal Investigator:

[name]-Consent Patient, Study Design, Data Collection and Data Analysis

Co Investigators

[name]-Consent Patient, Data Collection [name]-Consent Patient, Data Collection [name]-Consent Patient, Data Collection [name]-Consent Patient, Data Collection [name]-Study Design, Consent Patient, Data Collection [name]-Study Design, Consent Patient, Data Collection [name]-Consent Patient, Data Collection [name], CAA-Consent Patient, Data Collection

Hypothesis:

Periodic small volume boluses of diluted papaverine in peripheral arterial catheters of pediatric patients *will prevent* arterial spasm and help maintain patency of arterial catheters during general anesthesia.

Background:

What is the problem? -- Overdamping of arterial waveform and inability to aspirate from peripheral arterial catheters minimizing their utility in pediatric population undergoing general anesthesia for surgical procedures.

a) Pediatric patients undergoing complex surgical repairs or those with complex comorbidities often require continuous arterial pressure monitoring to help maintain hemodynamics and obtain blood samples to ensure optimal therapy. However, the accuracy of this system is subject to wide variability due to patient characteristics (caliber of the vessels), site of cannulation (radial versus posterior tibial), the type of catheter (size and material), and the catheter-tubing-transducer-flush system. We notice that maintaining the patency of peripheral arterial catheters in this age group is a difficult issue many pediatric anesthesiologists face, especially during lengthy surgical procedures or when temperature instability is present (cardiopulmonary bypass). Unfractionated Heparin, normal saline and papaverine have been shown to prolong patency of peripheral arterial catheters in neonates and children{Heulitt:1993un, Griffin:2005bo} when used in a continuous pump-based infusion in the intensive care setting. While the continuous infusion ensures patency of peripheral arterial catheters in an intensive care setting, this method is not convenient for use during surgery. Intraoperatively, the peripheral arterial catheter-tubing-transducer is usually connected to a pressurized bag of normal saline or heparinized saline (2 units/mL) allowing for continuous leaching up to 3 mL/hour.

What do we do at our institution currently?

Intraoperatively, peripheral arterial catheters are placed and secured by the pediatric anesthesia care team, and a pressurized heparin (2 units/mL) bag (500mL) is connected to the transducer to maintain patency. Towards the end of surgery, the pediatric anesthesia care team transitions the fast flush system to a continuous pump-based papaverine/heparin infusion system before transporting the patients to the intensive care unit. However, as rescue, the anesthesia care team frequently uses papaverine bolus (0.3 mg) in patients undergoing cardiac surgery to treat arterial spasm whenever arterial catheter spasm is suspected.

What is the advantage of adding papaverine bolus to arterial line catheter care during general anesthesia?

Papaverine is an alkaloid obtained from opium with a characteristic effect of relaxation of all smooth muscle, especially when spasmodically contracted. Papaverine acts directly on the muscle itself, unrelated to innervation, and the relaxation is prominent if spasm exists. The current standard of care is to administer papaverine after surgery to help relax the blood vessel and keep the catheter open for reliable blood pressure monitoring and sampling. There is evidence that papaverine infusion helps to relax arterial blood vessels in pediatric patients.

We do use this drug intraoperatively as a rescue with anecdotal evidence of relief of spasm. However, we do not know if administering papaverine bolus during surgery will *help prevent* or treat vasospasm. This study may help the study doctors learn things that may help other patients in the future.

[figure not shown]
With current practice and care of catheters in ICU, arterial catheters remain patent during standard infusions of papaverine. Adopting this strategy, we hypothesize that small volume boluses of papaverine/heparin (1mL of 0.12 mg/mL papaverine, heparin 2units/mL premixed syringe made by the pharmacy) during general anesthesia can maintain and prolong patency of these arterial catheters. This volume was chosen to mimic a one hour's dose of papaverine that the patient would have received as a continuous infusion in the ICU setting. See methods for more dosing details.

Study Method:

Prospective study- Parental consent will be obtained. The surgical list will be evaluated to review all patients age 0-17 years who would require elective placements of arterial catheters based on patients clinical complexity (ex. congenital heart disease) or based on the type of surgery (ex. open heart surgery)

Exclusion criteria:

- 1. Patients with a history of significant liver dysfunction.
- 2. Patients undergoing liver transplants.
- 3. Patients with Grade 2 or more of intraventricular hemorrhage.
- 4. All preterm patients with a gestational age less than 37 weeks at the time of surgery.

Randomization- A predetermined randomization list will be followed to allocate the patient to the treatment group or control group.

Double Blinding- The patients, patient's family, principal investigator, and the anesthesiology care team will be blinded to the allocation list.

Syringe Blinding- A member of the anesthesiology care team *not involved* in direct patient care will be given the randomizer list.

This team member will be given 2 syringes.

- 1. a) The 50mL premixed syringe of papaverine as dispensed from pharmacy (NaCl 0.9% inj 48.8 mL + papaverine 6mg+ heparin 100 units)
- 2. b) 10 mL of 2 units/mL of heparin from the pressurized fast flush bag from the operating room.

Based on the list, one of the below will be aspirated in a Research syringe

- 3. 1) 2 mL from the premixed-papaverine syringe will be aspirated in a sterile aseptic fashion in a 3 mL BD syringe and labelled as RESEARCH SYRINGE, with patient identifiers, date and time of constitution, expiry time and signature.
- 4. 2) 2 mL of heparinized solution from the 2 units/mL heparin syringe will be aspirated in a 3 mL BD syringe and labelled as RESEARCH SYRINGE, with patient identifiers, date and time of constitution, expiry time and signature.

Time of administration: (see Figure 1: Flowchart)

The arterial catheters of all patients will be connected to the pressurized heparin flush system. All patients will receive 1 mL volume bolus from the "research syringe" as soon as the arterial catheter is placed and secured. Subsequent bolus from the "research syringe" will occur one hour after initial bolus.

 An intention to treat with 0.3 mg of papaverine (0.1mL from the papaverine vial) will be considered by the anesthesiology care team, if the arterial catheter spasm/patency or waveform does not improve 10 minutes after the second "research syringe" bolus (1 hour after initial placement).

[figure not shown]
[figure not shown]

[figure not shown]
Figure 1. Flowchart

Data Collected:

(Routine standard operating procedure data)

- 1. Patient Demographics
 - a. gestational age
 - b. age at operation
 - c. weight at birth
 - d. weight at operation
 - e. primary diagnosis
 - f. other diagnosis (syndrome, ductal dependency)
- 2. Operative Variable
 - a. type of surgery
 - b. duration of surgery
- 3. Arterial Catheters
 - a. time of placement

[figure not shown]
- b. site of catheterization
- c. number of attempts
- d. localization technique
- e. catheter placement technique
- f. Size and material type of the arterial catheter
- g. tubing length from the catheter to transducer
- Filtering set on arterial monitoring at a frequency higher than the natural frequency. For example, if patients heart rate is 70bpm, then a Filter frequency of (70*10)/60=11 Hz and above will be set. For a heart rate of 140bpm, a Filter of 20Hz will be set.
- 4. Indicators of arterial waveform patency performed from baseline and then every 1 hour intraoperatively
 - a. color changes at catheter site (presence or absence of local axon reflex with fluid flushes after placement) when the arterial line is accessible
 - b. presence/ absence of a dicrotic notch (a distinct dicrotic notch implies system has good resolution at higher frequencies and is not overdamped)
 - c. ability to draw lab sample
 - i. Negative aspiration is easy and draws back freely without cavitation using a 3 mL BD syringe
 - ii. Negative aspiration is difficult (cavitation during negative aspiration, takes more than 30 seconds to draw 1 mL) using a 3 mL BD syringe
 - d. Square wave test-A fast flush system will be used. Pressure bag will be set to 300 mmHg and the resultant waveform will be recorded on paper
 - e. Presence of Oscillations- Yes/no, how many above baseline (there should be at least one bounce. If the system does not oscillate, then there is too much damping). There should be no more than two oscillations.
 - i. Amplitude of D1
 - ii. Amplitude of D12 (The amplitude of each oscillation is no greater than $\frac{1}{3}$ of previous oscillation)
 - iii. Arterial Blood pressure reading compared with NIBP measurement at times of measurement.
 - iv. Postoperatively, we will measure the duration of catheter patency (# hours/days) and the reason for discontinuation up to two days after the procedure.
- 5. Measurement of hemodynamics (HR, BP, ETCO2) before Papaverine/Heparin or Heparin bolus and at 1 min, 5min and 10 mins after bolus.

Primary Outcome:

1. Indicators of intraoperative arterial waveform patency as mentioned above in Data Collection section 4a to 4d

Data Handling and Record Keeping

All information will be kept strictly confidential and all data collection sheets will be kept in a binder which will be locked in the office of the principal investigator. A linking log will be

maintained to keep patient information separate from the data collection sheet. All data will be manually entered into a secure electronic database that will encrypted and password protected. (https://www.uth.edu/uthshare/)

Quality Control and Assurance

There are no plans to have ongoing third party monitoring. Data will be reviewed and audited internally to ensure that data is consistent, accurate and complete.

Sample Size:

Since this is a pilot study, we will collect data on 50 patients in each group. Based on the Cohen's d for an anticipated effect size of 0.5 (we will use anyone of the indicators of patency as mentioned above), desired power level of 0.8 and a probability level of 0.05, we will re-submit for a full trial.

The list of potential patients will be obtained daily from the operating room log. Care4 records and OR Tracking will be used to screen for patients. The research team will make contact with the family member while obtaining the surgical and or the anesthesia consent.

Study Risks:

Papaverine acts on all smooth muscle cells and relieves vascular spasm. It is metabolized by the liver. There are no perceivable risks from exposure to papaverine bolus as it is standard of care to subject all patients in ICU to continuous infusion of papaverine after OR to maintain patency of arterial catheter and has been well studied in neonates and pediatric patients {Griffin:2005bo, Boris:1998wp, Heulitt:1993un}. Side effects of papaverine can include nausea, headache, flushing, bleeding, or allergic reaction. These side effects are rare.

Data and Safety Monitoring:

[figure not shown]
This study will not have a formal data and safety monitoring board. All subjects will be monitored by the Investigators for any adverse events, though none are anticipated. All unanticipated problems (adverse events, protocol deviations) will be reported to the IRB as required in a timely fashion.

Ethics:

We are seeking IRB approval for this study from CPHS.

Discussion of risks and possible benefits of participating in this study will be provided to the subjects and their families. Consent forms describing in detail the study procedures, and risks are given to the subject and written documentation of informed consent is required prior to starting the study.

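### Open-label rescue with the study drug is allowed in both arms from about 70 minutes, while hourly primary patency readings run on past it with no rescue item in the readable data list

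*Protocol*

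**What the plan says.** **Study dose.** The Background gives the papaverine bolus as "1mL of 0.12 mg/mL papaverine, heparin 2units/mL premixed syringe made by the pharmacy". Study Method has a 2 mL research syringe drawn up for each patient. The first 1 mL is given when the catheter is secured, and the next bolus "will occur one hour after initial bolus".

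**Rescue.** Time of administration then adds: "An intention to treat with 0.3 mg of papaverine (0.1mL from the papaverine vial) will be considered by the anesthesiology care team", with the condition "if the arterial catheter spasm/patency or waveform does not improve 10 minutes after the second" research bolus. The sentence does not restrict rescue to one arm, and Study Method blinds the care team that decides on it. The Background describes this dose as a frequent rescue in cardiac surgery and says: "We do use this drug intraoperatively as a rescue with anecdotal evidence of relief of spasm".

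**Readings and endpoint.** Data Collected, item 4, schedules "Indicators of arterial waveform patency performed from baseline and then every 1 hour intraoperatively". The Primary Outcome is "Indicators of intraoperative arterial waveform patency as mentioned above in Data Collection section 4a to 4d". Neither place separates readings before rescue from readings after it.

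**What is collected.** The readable list covers demographics, operative variables, catheter details, patency indicators and hemodynamics. The nearest entry to a drug record is item 5, hemodynamics "before Papaverine/Heparin or Heparin bolus and at 1 min, 5min and 10 mins after bolus". It names the two study solutions, not papaverine from the vial.

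**The concern.** The trial asks whether papaverine keeps the line open better than heparin alone. The rescue is papaverine. A heparin-arm patient who is rescued has received 0.30 mg, more than a papaverine-arm patient who never needed rescue (0.24 mg). From then on, the reading of that line is no longer a reading of heparin alone.

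If papaverine works, more heparin-arm lines should fail and be rescued, and some of them should reopen. Under the Primary Outcome as written, a reopened line scores as patent at the next hourly reading, just like a line that never failed. The difference between arms then shrinks because the drug works. Sample Size says that a full trial will be submitted after this pilot, so a weakened signal could mislead that decision. The rescue frequency is also something the full trial would need to know.

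**Working it through.** **1. Study dose, reproducing the plan's concentration.** Study Method gives 6 mg papaverine in a 50 mL premixed syringe.
- Concentration: 6 / 50 = 0.12 mg/mL, which agrees with the Background.
- Two boluses: 2 × 1 mL × 0.12 mg/mL = 0.24 mg.

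**2. Rescue against study dose.**
- Rescue / total study dose: 0.3 / 0.24 = 1.25.
- Rescue / one bolus: 0.3 / 0.12 = 2.5.
- Cumulative dose after one rescue: heparin arm 0 + 0.30 = 0.30 mg; papaverine arm 0.24 + 0.30 = 0.54 mg.

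These totals count the research syringe and one rescue only. They leave out the papaverine/heparin infusion that current practice starts towards the end of surgery.

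**3. Timing.** Count the hourly readings from the first bolus (an assumption; baseline and first bolus both belong to catheter placement).
- Rescue check: 60 + 10 = 70 min.
- Baseline and hour-1 readings (0 and 60 min) precede the stated rescue point.
- Hour-2 reading at 120 min: 120 − 70 = 50 min after rescue may first be given.

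Hour 2 is also the first scheduled reading that can show the response to both study boluses.

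**4. Share of readings open to the problem.** Take a line still failing at the check, with readings at hours 1 to T. Hour 1 precedes rescue and hours 2 to T can follow it, so the share is (T − 1)/T. The protocol gives no durations, so T is assumed:

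| T (hours after first bolus) | Share of post-baseline readings that can follow rescue |
|---|---|
| 1 | 0 |
| 2 | 1/2 = 0.50 |
| 3 | 2/3 = 0.67 |
| 4 | 3/4 = 0.75 |
| 6 | 5/6 = 0.83 |

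This is exposure to the problem, for failing lines only. It is not a bias.

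**5. Effect on the difference.** Let f_H and f_P be the proportions of lines failing at the check in the heparin and papaverine arms. Let g be the proportion of failing lines that are rescued and reopened. Assume the same g in both arms, no new failures, and no recovery without rescue.
- Difference without rescue: f_H − f_P.
- Difference read from hour 2: f_H(1 − g) − f_P(1 − g) = (1 − g)(f_H − f_P).

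The difference is multiplied by 1 − g. The protocol gives neither f nor g. With g anywhere from 0 to 1, the result runs from no loss to complete loss of the later difference. Only the direction, toward no difference, can be stated.

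**The case against.** **The design is defensible.** Rescue is existing care, is open to both arms and is decided by a blinded team. Comparing the arms with rescue allowed is a legitimate treatment-policy comparison, and any distortion works against papaverine. This stands. A reader might infer that rescue should be barred or that the comparison is invalid, but the protocol supports neither. Even a treatment-policy result, though, cannot be interpreted without knowing who was rescued and when.

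**The SAP can deal with it.** It can for the analysis rule. It would still need the fact and time of rescue, and the data list is set out in the protocol.

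**The information is not really lost.** A reader might infer that rescue will go unrecorded, or that the state of the line before rescue cannot be recovered. The documents do not support that. Dose and time are probably in the anesthetic record. An hour-1 reading exists, so a line failing then is already recorded as failing. The trigger is itself a judgement, at about 70 minutes, that the line has not improved. A full 4a to 4d reading just before rescue would repeat the aspiration and flush on a line in suspected spasm, and it is not needed in order to count rescue as a failure.

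**The list may not be exhaustive.** It is headed as routine data and does not itemize the time or dose of the study boluses either. Figure 1, the flowchart to which the rescue paragraph belongs, could not be read and may mention rescue. Both points limit the finding to the readable text. They do not touch the Primary Outcome, which carries on through rescue without distinction.

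**The size is unknown.** That is correct. Frequent use in current cardiac practice is not a rescue rate under this protocol.

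**Conclusion.** The point holds in a limited form. Followed as written, the protocol allows 0.3 mg of papaverine, 1.25 times the whole study dose, in either arm from about 70 minutes. It then scores later hourly readings as if rescue had not happened. A failed heparin-arm line reopened in this way can count as patent from hour 2. Baseline and hour-1 readings are unaffected, and nothing is affected if surgery ends before hour 2.

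The expected direction is toward no difference, so the flaw would not manufacture a benefit for papaverine. It rests on two assumptions: that rescue reopens some lines, for which the protocol offers only anecdotal support, and that rescue is commoner in the heparin arm, which follows only if papaverine works. The effect on the between-arm difference cannot be sized from the document. The sponsor should make the change, but the fault does not invalidate the trial. Confidence is medium, because Figure 1 was not visible and the anesthetic record probably holds part of the missing information.

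**What to change.** Add an item 6 to Data Collected: *Rescue papaverine: yes/no, clock time, dose in mg, and the sign that triggered it (spasm, aspiration or waveform).*

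In the primary analysis, count a rescued line as loss of patency from the time of rescue. Report the as-observed (treatment-policy) readings as a sensitivity analysis. The rule may sit in the SAP, but it should be fixed before unblinding. A full 4a to 4d reading before rescue is optional and should not delay treatment.

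The cost is one extra data-sheet line and one extra analysis, with no added patients or visits. Because rescue is discretionary, this rule brings clinical judgement into the endpoint. The blinding of the care team keeps that judgement independent of allocation, and the recorded trigger lets it be checked.

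### The rescue line's 0.1 mL gives 0.3 mg papaverine only at 3 mg/mL, but the 50 mL premix recipe needs stock above 5 mg/mL

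*Protocol*

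**What the plan says.** Four places in the Protocol bear on the rescue dose.

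- **Rescue (Study Method, Time of administration).** If the catheter or waveform has not improved 10 minutes after the second study bolus, the care team considers "0.3 mg of papaverine (0.1mL from the papaverine vial").
- **Premix (Study Method, Syringe Blinding).** The source syringe for the papaverine arm is "The 50mL premixed syringe of papaverine as dispensed from pharmacy (NaCl 0.9% inj 48.8 mL + papaverine 6mg+ heparin 100 units").
- **Bolus rationale (Background, last paragraph before Study Method).** The study bolus is "1mL of 0.12 mg/mL papaverine, heparin 2units/mL premixed syringe made by the pharmacy". Its volume was chosen to match one hour's "dose of papaverine that the patient would have received as a continuous infusion in the ICU setting".
- **Current practice (Background).** The text says that "as rescue, the anesthesia care team frequently uses papaverine bolus (0.3 mg) in patients undergoing cardiac surgery to treat arterial spasm". It gives no volume.

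The visible text gives neither a strength for the rescue vial nor a dilution step for the rescue dose.

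**The concern.** The rescue line ties a mass to a volume and so fixes a concentration. The premix recipe also constrains the papaverine concentration, through the volume it leaves for the drugs. The two do not agree if they describe the same vial.

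A clinician who draws up by the millilitre figure would then give a child more papaverine than ordered. The rescue amount is the same for every patient aged 0-17 years and in both arms. The Study Risks section states "There are no perceivable risks from exposure to papaverine bolus as it is standard of care", and it rests that on the postoperative ICU infusion. A rescue larger than intended moves further from that reference. The plan has no formal data and safety monitoring board and no third-party monitoring, so little else in it would catch a wrong volume.

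**Working it through.** **Inputs.** From the rescue line: 0.3 mg and 0.1 mL. From the premix recipe: 50 mL syringe, 48.8 mL saline, 6 mg papaverine, 100 units heparin. From the bolus rationale: 0.12 mg/mL papaverine, 2 units/mL heparin, and 1 mL as one hour of ICU infusion. The vial strength and the heparin stock strength are not stated.

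**1. The premix figures reproduce at a 50 mL fill.**
6 mg / 50 mL = 0.12 mg/mL and 100 units / 50 mL = 2 units/mL, both as stated.

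**2. Strength implied by the rescue line.**
0.3 mg / 0.1 mL = 3 mg/mL. The vial cannot be the premix itself, since 0.1 mL x 0.12 mg/mL = 0.012 mg.

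**3. Strength required by the recipe.**
Volume left for both drugs: 50 - 48.8 = 1.2 mL. Heparin takes some of it, so the papaverine stock exceeds 6 / 1.2 = 5 mg/mL. If 48.8 is itself rounded (48.75 to 48.85 mL), the bound runs from 6 / 1.25 = 4.8 to 6 / 1.15 = 5.2 mg/mL, still well above 3. At 3 mg/mL the 6 mg alone would take 6 / 3 = 2.0 mL, which does not fit in 1.2 mL.

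**4. Dose in 0.1 mL if the vial is the premix stock.**
0.1 mL x 5 mg/mL = 0.5 mg as a strict lower limit, and 0.5 / 0.3 = 1.67. The volume that holds 0.3 mg is below 0.3 / 5 = 0.06 mL.

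The exact multiple depends on the heparin volume. The values below are assumptions that show the range. Stock = 6 / (1.2 - heparin volume).

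| Assumed heparin volume | Papaverine stock | Dose in 0.1 mL | Multiple of 0.3 mg |
|---|---|---|---|
| 0.1 mL | 5.45 mg/mL | 0.55 mg | 1.8 |
| 0.2 mL | 6.0 mg/mL | 0.60 mg | 2.0 |
| 0.5 mL | 8.6 mg/mL | 0.86 mg | 2.9 |
| 1.0 mL | 30 mg/mL | 3.0 mg | 10 |

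**5. Scale against the plan's own reference.**
In hours of ICU infusion, the intended rescue is 0.3 / 0.12 = 2.5 hours' worth and the delivered rescue more than 0.5 / 0.12 = 4.17. For a child in the papaverine arm, two boluses plus rescue should total 2 x 0.12 + 0.3 = 0.54 mg. The total would exceed 0.24 + 0.5 = 0.74 mg, over 0.74 / 0.54 = 1.37 times as much.

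**6. The overfill alternative.**
With 3 mg/mL stock, the syringe holds at least 48.8 + 2.0 = 50.8 mL before heparin. Then papaverine is at most 6 / 50.8 = 0.118 mg/mL and heparin at most 100 / 50.8 = 1.97 units/mL, which still round to 0.12 and 2. In that case the rescue line is right and each 1 mL study bolus is at least 1.6% below 0.12 mg (0.1181 / 0.12 - 1 = -1.6%).

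**The case against.** The strongest reply is that each line is consistent on its own, and that the conflict needs two things the Protocol never says: a shared stock and an exact 50 mL fill.

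- **Separate product.** Pharmacy makes the premix, while the care team gives the rescue, so the two may draw on different products. A separate 3 mg/mL vial or a pre-dilution would make the rescue line correct. Figure 1, which was not visible in the text reviewed, may say so.
- **Nominal fill.** The 50 mL may be a nominal size. With 3 mg/mL stock, any total up to 6 / 0.115 = 52.17 mL still rounds to 0.12 mg/mL, with heparin at 100 / 52.17 = 1.92 units/mL, which rounds to 2. That leaves 52.17 - 50.8 = 1.37 mL for heparin, so heparin stock of about 73 units/mL or more would satisfy every stated concentration.
- **Limited consequence.** The order leads with the mass, rescue is only considered, and the Protocol gives no toxicity threshold.

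These points stand as possibilities, and they are why the error cannot be called proven. The visible text supports none of the escapes, however. It refers to a single papaverine vial without qualification and mentions no second product or dilution. Saline stated to 0.1 mL, with concentrations that match 50 mL exactly, favours a true 50 mL fill. An overfill would put that recipe out by at least 0.8 mL, so with shared stock a different line would need correcting.

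Rounding of the 0.1 mL does not help either. Stock of 5 to 6 mg/mL would need 0.06 to 0.05 mL for 0.3 mg, which rounds to 0.1 mL, but a clinician who drew 0.1 mL would still give 0.5 to 0.6 mg.

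**Conclusion.** The concern holds as a probable, not proven, dosing error that should be fixed. It rests on two assumptions: the rescue vial is the premix stock, and the premix is filled to 50 mL. Under both, the stated 0.1 mL delivers more than 1.67 times the order, and the Protocol sets no upper limit because the heparin strength is not given. The tenfold case needs an assumed heparin stock of 100 units/mL and should not be read as an estimate.

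Because 0.3 mg also appears as current practice, the volume is the likelier error. A wrong dose reaches a patient only if rescue is given and drawn up by volume, and harm at that dose is not shown. The randomized bolus would be affected only under the overfill reading, and then only slightly. Allocation and sample size play no part.

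**What to change.** Have pharmacy confirm the strength of the rescue vial and of the papaverine stock used for the premix. Keep 0.3 mg as the governing order, and then make the one change that fits the answer:

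- **Vial above 5 mg/mL:** replace 0.1 mL with the matching volume (under 0.06 mL), or specify a labelled 3 mg/mL dilution, for which 0.1 mL is correct.
- **Separate 3 mg/mL product:** keep 0.1 mL and write that strength in the rescue line.
- **Vial of 3 mg/mL that is also the premix stock:** correct the saline volume in the recipe instead, to 50 - 2.0 = 48.0 mL less the heparin volume.

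The cost is one pharmacy check and one corrected dosing line in a minor amendment.

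### The monitor filter is meant to sit above the natural frequency but is set from heart rate alone, so the rule permits a cut-off that distorts the square-wave reading

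*Protocol*

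**What the plan says.** The filter instruction closes item 3 (Arterial Catheters) of Data Collected in the Protocol. It gives a principle and then two worked examples.

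- Principle: "Filtering set on arterial monitoring at a frequency higher than the natural frequency".
- First example: "if patients heart rate is 70bpm, then a Filter frequency of (70*10)/60=11 Hz and above will be set".
- Second example: "For a heart rate of 140bpm, a Filter of 20Hz will be set".

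No value in Hz is given for the natural frequency, and no step measures it or compares the filter with it. Under Background, the protocol attributes variability in accuracy to patient characteristics, cannulation site, "the type of catheter (size and material), and the catheter-tubing-transducer-flush system"; heart rate is not named. Item 3g records "tubing length from the catheter to transducer", but the filter rule does not use it.

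The outcomes that read the filtered trace are in item 4. For 4b, "a distinct dicrotic notch implies system has good resolution at higher frequencies and is not overdamped". For 4d, the fast-flush test, "Pressure bag will be set to 300 mmHg and the resultant waveform will be recorded on paper". Item 4e interprets the flush trace: "If the system does not oscillate, then there is too much damping". The Primary Outcome section names items 4a to 4d, so 4e lies formally outside it, although it is how the 4d trace is judged.

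**The concern.** The natural frequency is a property of the plumbing: catheter, tubing, transducer and flush system. It is the frequency at which the trace rings after a flush. Ten times the pulse rate is a different quantity, namely the bandwidth needed to reproduce that patient's pulse up to its tenth harmonic. Meeting one condition does not imply meeting the other.

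This matters because the flush test excites the system at its own frequency. A low-pass filter with its cut-off below that frequency shrinks the oscillations that item 4e looks for, and 4e reads missing oscillation as overdamping. A filter setting can therefore push the reading towards overdamped with no change in the artery or catheter. Because the rule moves with heart rate and patients are aged 0 to 17 years, the setting can also differ between patients for reasons unrelated to patency.

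At stake is how well primary item 4d, and possibly 4b, measures patency in a pilot of 50 patients per group. The Sample Size section would let any one of the patency indicators supply the effect size for a full trial.

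**Working it through.** **1. The protocol's own figures.** The rule is filter = HR × 10 / 60.

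- 70 bpm: 70 × 10 / 60 = 11.67 Hz. The protocol states 11 Hz, as a minimum.
- 140 bpm: 140 × 10 / 60 = 23.33 Hz. The protocol states 20 Hz, as a single value. 20 Hz is what the rule gives at 120 bpm.

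The two examples do not come from one formula. Correcting that would not settle the present point, which concerns what the formula is built on.

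**2. When the rule meets its aim.** The computed filter exceeds a natural frequency fn only if HR × 10 / 60 > fn, that is HR > 6 × fn.

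| Natural frequency (assumed) | Heart rate above which the computed filter exceeds it |
|---|---|
| 10 Hz | 60 bpm |
| 15 Hz | 90 bpm |
| 20 Hz | 120 bpm |
| 25 Hz | 150 bpm |
| 30 Hz | 180 bpm |

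So at 70 bpm the computed minimum misses the aim for any fn of 11.67 Hz or more. At 140 bpm the stated 20 Hz misses it for any fn of 20 Hz or more.

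**3. Effect on the flush trace.** These inputs are assumptions, none given in the protocol: a second-order catheter system, fn of 15 to 25 Hz, damping ζ = 0.2, and a second-order Butterworth low-pass filter. The unfiltered first overshoot is exp(−πζ/√(1−ζ²)) = exp(−0.641) = 0.527 of the step. Passing the step response through the filter gives this first overshoot:

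| Filter | fn 15 Hz | fn 20 Hz | fn 25 Hz |
|---|---|---|---|
| none | 52.7% | 52.7% | 52.7% |
| 11.67 Hz | 30.5% | 16.9% | 5.8% |
| 20 Hz | 47.5% | 40.1% | 31.7% |
| 40 Hz | 52.7% | 52.0% | 50.2% |

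**4. Sensitivity to the assumptions, filter at 11.67 Hz.**

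- First-order filter, ζ = 0.2: 26%, 16% and 8% for 15, 20 and 25 Hz. A first-order filter at 40 Hz leaves 49%, 46% and 44%.
- Second-order filter, ζ = 0.3 (unfiltered 37%): 22%, 12% and 5%.
- Second-order filter, ζ = 0.4 (unfiltered 25%): 16%, 9.5% and 5%.
- fn only just above the cut-off (12 Hz, ζ = 0.2, second-order): the first overshoot is still 39% and the next swing 19%, against 53% and 28% unfiltered.

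The loss is large when fn is about twice the cut-off (25 / 11.67 = 2.1) and moderate when the two are close.

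**5. Which outcomes are exposed.** Items 4d and 4e read the flush trace directly. Item 4b reads the notch on the same filtered trace, but no notch calculation was made. Items 4a (colour change) and 4c (aspiration) do not pass through the filter.

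**The case against.** The strongest reply is that the 70 bpm figure is a floor. A team that sets 20 or 40 Hz at 70 bpm complies with the example, and read together with the principle it would have to go higher whenever the natural frequency is higher. That stands: the text permits a low filter and does not force one. The 140 bpm example, however, has no such allowance, and a floor without a fixed value leaves the setting to each operator.

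Natural frequency may also be loose wording for the tenth harmonic. That would explain the sentence but not cure the measurement, since the flush still rings at the system's own frequency.

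The size rests on assumed values, and the ζ = 0.2 system is not clearly a sound one. Its successive swings have ratio 0.277 / 0.527 = 0.53, above the one-third limit in item 4e.ii unless that limit is read from full cycle to full cycle (0.28). That is fair. At ζ = 0.4, where the swing ratio is 0.25 and the limit is met, the overshoot is still reduced from 25% to between 16% and 5%.

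A reader might go further and infer four things that the protocol does not support:

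- That good catheters will be recorded as overdamped. Item 4e asks for at least one bounce. Under the main assumptions 31% and 17% overshoots remain at 15 and 20 Hz, and the bounce nearly vanishes only at 25 Hz.
- That a change in heart rate during surgery would pass for a change in patency. The filter is listed with the catheter characteristics in item 3, not among the hourly readings in item 4, and no text says that it is reset.
- That the notch in 4b is lost. A cut-off at ten times the pulse rate scales with the pulse, and loss of the notch has not been shown.
- That the treatment comparison is biased. The rule is the same in both blinded arms, so the error is probably non-differential.

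**Conclusion.** The point holds as a gap between the stated aim and the working rule. The filter is to exceed the natural frequency, but it is fixed by heart rate alone and never compared with that frequency. The rule therefore permits a cut-off at or below it and lets the setting vary between patients.

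The size is conditional. If the natural frequency is below 11.67 Hz, the computed settings at 70 bpm and above meet the aim. If it is 15 to 25 Hz and the filter sits at the 70 bpm minimum, the first overshoot falls from 53% to between 31% and 6% (damping 0.2, second-order filter); with a 20 Hz filter it is 48% to 32%. The expected consequence is a diluted comparison on 4d, possibly on 4b, and a reading that depends partly on the filter. It is a modest measurement fault, worth correcting because correction is nearly free.

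**What to change.** In Data Collected, item 3, delete the heart-rate formula and both examples. State one fixed filter setting for all patients and all readings, high enough to exceed the natural frequency (for example, the highest the monitor offers), and record it on the data sheet. Check it against the natural frequency read from the spacing of the oscillations on the square-wave trace that item 4d already puts on paper, with the trace taken at that fixed setting.

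This also removes the mismatch between the 70 and 140 bpm examples. The cost is one sentence in the protocol and one recorded field, with no new procedure. The downside is slightly more high-frequency noise on the trace. The protocol does not say which settings the monitor offers, so the sponsor should confirm that a suitable one exists.
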